#### 4.1.2 Subgroups of interest

Subgroups defined by levels of sex  
Subgroups defined by levels of race/ethnicity  
Subgroups defined by levels of HIV status  
Subgroups defined by presence (or absence) of advanced disease on chest x-ray conducted at screening.

#### 4.1.3 Interim Monitoring

##### 4.1.3.1 Early Assessment of QT Prolongation

After 12 Arm 1 participants have evaluable AE data through week 2, we will find the point estimate of the proportion of participants in the ITT population on Arm 1 with prolonged QT interval (defined by  $QTcF > 500$  ms) and corresponding two-sided Pearson-Klopper exact 95% confidence interval.

##### 4.1.3.2 Interim Futility Analysis

Note: Due to the early closure to accrual, this analysis will not be conducted.

We will estimate the conditional power of the test statistic at the second DSMB review using two methods in the efficacy set.

- 1) Under the assumption that the future data follows the hypothesized difference between Arm 1 and Arm 2 (hazard ratio of 1.8 between arms).

- 2) Under the assumption that future data follows the estimated difference between Arm 1 and Arm 2 at the time of the review (the estimated hazard ratio).

#### **4.1.3.3 Unfavorable Composite Outcome Monitoring in Arm 1**

We will find the two-sided 95% confidence bands for cumulative unfavorable outcome probabilities in Arm 1 in the safety set approximately one month after the first participant completes treatment, and will continue approximately monthly and for each DSMB review until the end of the study. We will present these estimates alongside historical unfavorable proportions for SOC on the REMox, OFLOTUB, RIFAQUIN, and Study31 trials, and A5362 SOC data as available. There will be no adjustment to the confidence bands for multiple looks.

#### **4.1.3.4 Early Recurrence Monitoring in Arm 1**

We will find the two-sided 95% confidence bands for cumulative relapse probabilities in Arm 1 beginning approximately 2 months after the first participant completes treatment, and will continue approximately monthly and for each DSMB review until the end of the study. We will present these results alongside historical relapse proportions for SOC on the REMox, OFLOTUB, and RIFAQUIN trials, and A5362 SOC data as available. There will be no adjustment to the confidence bands for multiple looks.

## 5 Analysis Approaches

### 5.1.1 Primary Estimands

Primary Objective 2.3.1.1: To compare time to 12-week liquid culture conversion for Arm 1 with SOC controls (Arm 2)	
Estimand description	Time to liquid culture conversion through 12 weeks of follow-up among individuals aged ≥18 years and with pulmonary TB without demonstrated isoniazid or rifampicin resistance.
Treatment	13-week Experimental Regimen: rifapentine/isoniazid/pyrazinamide/ethambutol (PHZE) + clofazimine (CFZ)  26-week Standard of Care: rifampicin/isoniazid/pyrazinamide/ethambutol (RHZE) followed by rifampicin/isoniazid (RH)
Target population	Analysis set
Individuals aged ≥18 years living with confirmed pulmonary TB without demonstrated isoniazid or rifampicin resistance.	Efficacy set (All participants who are randomized to study treatment and are not late exclusions)
Variable	Outcome measure 3.1.1
Time to stable culture conversion based on sputum samples taken at serial collections up to 13 weeks after treatment initiation.  Note: The time of stable culture conversion will be the time of the sampling date of the first of two culture negative sputum samples in liquid media (MGIT) without an intervening positive culture. We also consider a participant's inability to produce sputum with no signs of active TB at a given visit as a negative sputum culture. A negative culture at week 13 can be used as the confirmatory second culture to determine stable culture conversion at week 12.	Time to stable culture conversion in liquid media, defined as the first of two (consecutive or non-consecutive) negative sputum cultures without an intervening positive culture, and/or visits wherein the participant is unable to produce sputum and has no signs of active TB, up to 12 weeks post-randomization.
Handling of intercurrent events	Handling of missing data
The following intercurrent events are relevant to the estimand:  1. Failure to start TB treatment Observations will be used to determine the variable (treatment policy strategy)  2. Premature treatment discontinuation due to suspected TB treatment failure or TB recurrence or poor treatment response. Observations will be used to determine the variable (treatment policy strategy)  3. Premature TB treatment discontinuation due to TB death Observations will be used to determine the variable (treatment policy strategy)  4. Premature treatment discontinuation for other reason Observations will be used to determine the variable (treatment policy strategy)  5. Non-TB death	Participants who have contaminated or missing samples leading up to and including week 12 will be censored at the last sampling date for which they had a valid sputum culture assessment.  Participants who experience premature TB treatment discontinuation due to TB death will be censored at week 12.

Observations will be used to determine the variable (treatment policy strategy)	
Population-level summary measure	Analysis approach
Hazard ratio of culture conversion through 12 weeks of follow-up.	
We will estimate the treatment effect with a hazard ratio and corresponding 90% two-sided confidence interval. We consider Arm 1 superior to Arm 2 if the one-sided p-value is less than 0.05 in favor of Arm 1. The hazard ratio (HR) will be estimated from a Cox proportional-hazards model, with HIV status (positive; negative) and advanced disease according to chest X-ray (yes/no) treated as stratification factors. We will assess the proportional hazards assumption visually by plotting the scaled Schoenfeld residuals against the natural logarithm of the time to event. In the event that the data violate the proportional hazards assumption, we will conduct the primary analysis with a stratified log-rank test.
 
Participants who do not achieve stable culture conversion, but who are on study and have contaminated or missing cultures leading up to and including week 12 will be censored at the last sampling visit for which they had a valid sputum culture assessment. Participants who are lost to follow-up prior to 12 weeks with their last culture being positive will be censored at 12 weeks (i.e. assumed they did not have a culture conversion by week 12), and participants who are lost to follow-up prior to 12 weeks with their last culture being negative will be censored at the last sampling visit for which they had a valid culture result. Participants who die prior to week 12 will be censored at 12 weeks.

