## **2.3 Study Objectives**

This Primary SAP addresses the following primary and secondary objectives listed in the study protocol. We address other study objectives outlined in the protocol in subsequent secondary analysis plans.

We will analyze the primary efficacy objective below (2.3.1.1) using a superiority framework based on a one-sided 0.05 alpha level test. For analyses of other objectives, we will present estimates of the parameter of interest alongside their respective two-sided confidence intervals, as specified in Section 5.

We will finalize all analyses for the primary analysis report once the last enrolled participant has completed the week 26 study visit and all queries have been resolved.

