### 2.3.2 Secondary Objectives

Each is a comparison between Arm 1 and Arm 2 unless otherwise specified.

- 2.3.2.1 To compare proportion of participants who experience a favorable composite efficacy outcome at 65 weeks between Arm 1 and Arm 2 participants
- 2.3.2.2 To compare premature regimen discontinuation (tolerability) between Arm 1 and Arm 2 participants
- 2.3.2.3 To estimate and compare CFZ-associated increases in QT interval (QTcF, using the Fridericia correction)
- 2.3.2.4 To estimate and compare time to stable liquid and solid mycobacterial culture conversion
- 2.3.2.5 To compare proportion of participants with liquid and solid culture conversion at weeks 8 and 12 between Arm 1 and Arm 2 participants
- 2.3.2.6 To compare days to positivity in automated liquid mycobacterial culture over treatment time
- 2.3.2.7 To compare chest radiographic score (with specific attention to resolution of cavitary disease) between Arms from baseline to end of treatment (Arm 1, week 13; Arm 2, week 26) between Arm 1 and Arm 2 participants
- 2.3.2.8 To compare proportions of participants who experience a favorable clinical/bacteriologic treatment outcome at 65 weeks between Arm 1 and Arm 2 participants
- 2.3.2.9 To estimate cumulative relapse and recurrence proportions up to week 65 for participants on Arm 1 and Arm 2
- 2.3.2.10 To determine CFZ pharmacokinetic (PK) parameters in plasma in Arm 1
- 2.3.2.11 To compare PK parameters when CFZ is given with a loading dose in Arm 1 and without a loading dose in Arm C
- 2.3.2.12 To objectively and subjectively assess CFZ-associated skin hyperpigmentation between Arm 1 and Arm 2 participants

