## 2.4 Overview of Sample Size Considerations

We plan to enroll a total of 185 participants; approximately 110 in Arm 1, 55 in Arm 2, and 20 in Arm C. We estimate that we will have at least 90% power to detect an effect between Arm 1 and Arm 2 with respect to the primary efficacy outcome. We assume 70% culture conversion by week 12 in Arm 2 and a hazard ratio of 1.8. We use a 2:1 allocation ratio and assume that 10% of participants will have unevaluable culture conversion results.

For the primary safety outcome, we will compare proportions of participants with any Grade 3 or higher adverse events (AE) between Arms. Table 10.4-2 from the study protocol (copied below) gives the power we would have to detect that Arm 1 is inferior to Arm 2 assuming a two-sided type 1 error of 0.10, 10% probability of developing an AE in the SOC Arm, and varying probabilities (15-30%) of developing an AE in experimental Arm. We also provide the 90% confidence interval (CI) width for the comparison.

Protocol Table 10.4-2

Power	N1	N2	N	Arm 1 Proportion with $\ge$ Grade 3 AE	Arm 2 Proportion with $\ge$ Grade 3 AE	Two-sided type 1 error	90% CI Width
0.13	100	50	150	0.15	0.10	0.10	0.210
0.36	100	50	150	0.20	0.10	0.10	0.218
0.64	100	50	150	0.25	0.10	0.10	0.225
0.85	100	50	150	0.30	0.10	0.10	0.230

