#### 4.1.1 Analysis set definitions

##### 4.1.1.1 Analysis sets (used for primary (5.1.1) and key secondary (5.1.2) estimands):

- **Efficacy Set:**  
All participants who are randomized to study treatment and are not late exclusions.  
(Participants will be late exclusions if they do not have any positive culture (liquid or solid) at screening, entry, or week 1, or if they have TB that is RIF-resistant or INH-resistant identified at screening or entry.)
- **Safety Set:**  
All participants who start assigned study treatment.
- **Start treatment/not late exclusion set:**  
All participants who start assigned study treatment and are not late exclusions.
- **Alive/adequate treatment set:**  
All participants who complete an adequate course of treatment as defined within Sections 10.2.5 and 10.2.6 of the protocol and who do not die during treatment.
- **Per protocol Set:**  
All participants who start and complete assigned study treatment.

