### 6.2 Baseline Characteristics

- Summary of age, sex, gender, country, Karnofsky Score (50-70, 80-100), BMI, HIV Status (stratification factor), advanced disease status determined by chest x-ray (stratification factor), Total CES Depression Scale Score, CD4 count among those HIV positive, viral load among those HIV positive
- Baseline TB diagnostic test results (AFB smear, drug susceptibility tests)
- Baseline lab results for AST, ALT, bilirubin, hemoglobin
- 2x2 table displaying concordance of site classification and central reader classification of advanced disease status by chest x-ray

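### The primary culture-conversion Cox model leaves out baseline mycobacterial load: a missed efficiency gain, not a bias or a power error

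*SAP*

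**What the plan says.** The primary efficacy objective is tested "using a superiority framework based on a one-sided 0.05 alpha level test" (SAP 2.3). All other objectives get estimates with confidence intervals. Section 5.1.1 fits a Cox model "with HIV status (positive; negative) and advanced disease according to chest X-ray (yes/no) treated as stratification factors". These are the two factors that stratify the randomization (SAP 2.1). If proportional hazards fails, the analysis switches to a stratified log-rank test.

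Section 5.1.1 lists no sensitivity analysis for this estimand. The supplemental analyses are interaction models for sex and for race/ethnicity, with the same two factors, and a restricted mean time comparison at 12 weeks. None uses baseline load.

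Baseline measures related to load appear elsewhere in the SAP:

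- Section 6.2 tabulates "Baseline TB diagnostic test results (AFB smear, drug susceptibility tests".
- Section 4.1.1.1 makes participants late exclusions "if they do not have any positive culture (liquid or solid) at screening, entry, or week 1", so screening and entry sputum is cultured.
- Objective 2.3.2.6 is "To compare days to positivity in automated liquid mycobacterial culture over treatment time". The matching outcome, 3.2.6, lists visits from week 1 on and names no baseline value.

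Section 2.4 claims "at least 90% power to detect an effect between Arm 1 and Arm 2" and states: "We assume 70% culture conversion by week 12 in Arm 2 and a hazard ratio of 1.8". It does not say whether 1.8 is conditional on any covariate.

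**The concern.** The endpoint is the time until sputum turns and stays culture-negative in liquid medium. The amount of mycobacteria in sputum at the start is the baseline state of that same process, so it is the natural candidate for a prognostic covariate. A yes/no X-ray reading can stand in for it only roughly.

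In a Cox model, leaving out a prognostic covariate moves the estimated hazard ratio closer to 1 than the ratio at fixed covariate value, and the test has less power than one that adjusts. This is the trial's only formal superiority test. Accrual closed early (SAP 2.1; Protocol Letter of Amendment #1), so fewer than the planned 110 + 55 may contribute, and efficiency is worth more than at design. The final number is not given.

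**Working it through.** **1. Inputs from SAP 2.3 and 2.4.** One-sided alpha 0.05; 110 v 55 participants, 10% unevaluable, so 99 v 49.5; 70% conversion by week 12 in Arm 2; HR 1.8.

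**2. The plan's own figure.** Under proportional hazards, Arm 1 conversion is 1 − 0.3^1.8 = 0.8855. Events = 99 × 0.8855 + 49.5 × 0.70 = 87.7 + 34.65 = 122.3. Schoenfeld: z = √(122.3 × 2/3 × 1/3) × ln 1.8 − 1.645 = 5.213 × 0.588 − 1.645 = 1.42, so power is 92.2%. Ninety percent needs 112 events. The claim reproduces, and this calculation uses no load term.

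**3. Simulation set-up (assumptions, not in the documents).** Two models were fitted to each simulated trial of 99 v 50, both stratified by HIV and X-ray with stratum-specific baseline hazards h₀ₛ(t):

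- planned: h₀ₛ(t)·exp(θA)
- adjusted: h₀ₛ(t)·exp(θA + γZ)

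A is the arm and Z is standardized baseline load. Conversion was recorded at weeks 1, 2, 3, 4, 6, 8, 10 and 12, with Efron ties. HIV prevalence was 30% with no effect. Z had correlation 0.4 with the latent variable behind the X-ray factor. Each scenario had 1,000 to 1,500 trials, so near 91% the standard error is about 0.7 to 0.9 points (for example √(0.908 × 0.092/1500) = 0.0075).

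**4. If 1.8 is the HR that the planned model estimates:**

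| Log-HR per SD of load | HR per SD | Planned | Adjusted | Gain (points) |
|---|---|---|---|---|
| 0.2 | 1.22 | 90.6% | 91.9% | 1.3 |
| 0.4 | 1.49 | 90.5% | 93.8% | 3.3 |
| 0.6 | 1.82 | 91.0% | 95.6% | 4.6 |
| 0.8 | 2.23 | 90.8% | 97.5% | 6.7 |

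A second simulation (2,400 trials per row, Weibull times, HIV 20%) agrees. At log-HR 0.30, 0.43, 0.60 and 0.74, power is 90.7, 91.1, 90.8 and 91.6% without load and 92.3, 93.9, 96.3 and 97.5% with it.

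**5. If 1.8 is instead the HR at fixed load:**

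| Log-HR per SD | Planned: HR, power | Adjusted: HR, power |
|---|---|---|
| 0 | 1.80, 90.5% | 1.81, 90.2% |
| 0.2 | 1.78, 88.7% | 1.80, 89.2% |
| 0.4 | 1.71, 83.6% | 1.77, 88.1% |
| 0.8 | 1.58, 70.8% | 1.78, 86.8% |

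The first row is the case where load has no prognostic value. Its 0.3-point difference is inside simulation error.

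**6. If the X-ray factor captures more of the load (correlation 0.7, same reading as step 5).** At 0.4 the gain falls from 88.1 − 83.6 = 4.5 points to 89.7 − 86.5 = 3.2. At 0.8 it falls from 86.8 − 70.8 = 16.0 to 87.9 − 75.5 = 12.4.

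**7. Type I error with no treatment effect (log-HR per SD 0.4 and 0.8).** Planned 4.4% and 5.7%; adjusted 5.0% and 4.6%. The standard error is √(0.05 × 0.95/1000) = 0.7 points, so both models hold the 5% level.

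**8. Smaller trial.** At 60 v 30 evaluable (an illustration only), under the reading in step 4, the second simulation gives 73% v 77% at log-HR 0.43 and 75% v 87% at 0.74.

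These gains assume that load itself enters the model. A coarse or noisy proxy such as smear would recover only part of them.

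**The case against.** The case for leaving the model alone is substantial. It matches the randomization strata, holds its type I error, and delivers the stated power. Three stronger readings are tempting, and the documents support none of them.

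- *The planned hazard ratio is biased toward 1.* The shift in step 5 is non-collapsibility. The two-factor ratio is a legitimate estimand, different from the load-conditional one, and SAP 5.1.1 does not claim the latter.
- *The trial has well under 90% power.* That needs 1.8 to be the ratio at fixed load, which SAP 2.4 does not say. If 1.8 belongs to the planned model, nothing stated is lost.
- *Baseline MGIT days to positivity is already a trial variable.* It can only be inferred: outcome 3.2.6 starts at week 1, and SAP 6.2 names smear without saying that it is graded.

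Four practical objections also stand, and they shape the fix. The Efficacy Set admits people positive only on solid medium or only at week 1, who have no positive baseline liquid culture. Substituting smear for days to positivity within one covariate would mix scales. The log-rank fallback cannot carry the covariate. The trial is open-label, and Arm 1's high failure and recurrence rate was known by June 2023, before SAP version 3.0 (October 13, 2023), so a late change to the primary model could look data-driven.

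The protocol file supplied is Letter of Amendment #1. The base protocol might give a reason for the choice of covariates, so the absence of one here is weak evidence. Accrual also stopped because of treatment failure and recurrence, and the documents do not show that a decision now turns on a few points of power for 12-week conversion. This limits the point's weight. It does not remove it, because adjustment costs essentially nothing when load is uninformative.

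**Conclusion.** The point holds as a missed efficiency gain. The primary model is valid, but it uses only two binary factors and ignores a baseline measure closely tied to the endpoint. The trial collects that measure at least as smear and as screening and entry culture.

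At 99 v 50, with 1.8 read as the planned model's hazard ratio, the gain is about 1 to 7 points of power (from about 91% to between 92% and 97.5%), and effectively zero if load is not prognostic. It is smaller if the X-ray factor already captures load or if the covariate measures load poorly. The prognostic strength of load, its correlation with the X-ray factor and the HIV prevalence are all assumptions. Only the 92.2% rests on the plan's own inputs.

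**What to change.** In the SAP 5.1.1 analysis approach, keep the two strata and add one baseline-load covariate, chosen in advance and on a single scale:

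- baseline AFB smear result as a categorical term with a missing category; or
- baseline MGIT days to positivity, if it is recorded at screening or entry, with culture-negative baselines coded at the upper limit and an indicator for missing or contaminated results.

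Use screening or entry samples only, because week 1 follows randomization. Either rule keeps every member of the Efficacy Set in the model.

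Report the current two-factor model alongside. State that the log-rank fallback stays stratified on the two factors without the covariate. Section 5.1.3.3 borrows this approach for conversion through week 26, so say whether the covariate carries over.

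Settle this before any by-arm culture-conversion data are analysed, and record that this was so. If those data have already been seen, keep the current model as primary and add the load-adjusted Cox model to the Supplemental Analyses of 5.1.1.

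The cost is SAP wording and a baseline variable in the analysis dataset, with no new participants or samples. The downsides are that the reported hazard ratio becomes conditional on baseline load as well as the strata, and that a missing-baseline rule is needed.

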### Sensitivity Analyses

None.

### Supplemental Analyses

We will also test the treatment by sex and treatment by race/ethnicity interaction terms in separate Cox proportional hazards models. These models will also include the same stratification factors as the primary analysis: HIV status and advanced disease according to chest X-ray reading. In a supplemental analysis, we will estimate the difference in restricted mean survival times (difference in restricted mean time to culture conversion) for a time horizon of 12 weeks.

Primary Objective 2.3.1.2: To compare the proportion of adverse events (safety) over 65 weeks between Arm 1 and Arm 2	
Estimand description	Probability of having at least one grade 3 or higher adverse event through 65 weeks that is at least a one-grade increase from baseline among patients aged $\geq 18$ years living with pulmonary TB without demonstrated isoniazid or rifampicin resistance.
Treatment	13-week Experimental Regimen: rifapentine/isoniazid/pyrazinamide/ethambutol (PHZE) + clofazimine (CFZ)  26-week Standard of Care: rifampicin/isoniazid/pyrazinamide/ethambutol (RHZE) followed by rifampicin/isoniazid (RH)
Target population	Analysis set
Patients aged $\geq 18$ years living with pulmonary TB without demonstrated isoniazid or rifampicin resistance who initiate TB therapy.	Safety Set (All participants who start their assigned study treatment)
Variable(s)	Outcome measure 3.1.2
Occurrence of a Grade 3 or higher adverse event through 65 weeks that is new in onset or aggravated in severity of frequency from the baseline condition.	Proportion across study arms experiencing any Grade 3 or higher AE that is at least a one-grade increase from baseline over 65 weeks.
Handling of intercurrent events	Handling of missing data

 
1. Persistent clinical disease and extension of treatment Observations will be used to determine the variable (treatment policy strategy)
 
2. Premature treatment discontinuation Observations will be used to determine the variable (treatment policy strategy)
 
3. Premature treatment discontinuation due to suspected TB treatment failure or TB recurrence or poor treatment response. Observations will be used to determine the variable (treatment policy strategy)
 
	Participants who discontinue follow-up before week 65 will have their outcome determined based on data available until the time of discontinuation (i.e., missing observations after discontinuation that would be relevant to the variable are considered missing completely at random).  Sensitivity analyses will consider participants who discontinue follow-up before week 65 as having at least one Grade 3 or higher adverse event that is at least a one-grade increase from baseline.
Population-level summary measure	Analysis approach
Probability of having at least one Grade 3 or higher AE that is at least one-grade increase from baseline at any time during the 65 weeks after treatment initiation.	We will compare the cumulative proportion of participants experiencing a Grade 3 or higher AE that is at least one-grade increase from baseline at any time during the 65-week study period between Arm 1 and Arm 2 using the Kaplan-Meier estimator at week 65. Participants who have not experienced an event will be censored at the last completed study visit. For participants who experience more than one event, we will use the time of the first occurrence as the time of event. We will present the point estimate and 90% two-sided confidence intervals for the difference in cumulative proportions.

Supplemental Analyses:

As supplementary analyses, we will also estimate the Kaplan-Meier proportions and confidence intervals for the outcome measure up to week 13, and up to week 26. These time horizons correspond to the end of treatment for Arm 1, and Arm 2, respectively.

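### The sensitivity analysis for the primary safety comparison counts dropouts in both arms as events, so it does not bound the Arm 1 minus Arm 2 difference

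*SAP*

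**What the plan says.** SAP Section 5.1.1 (Primary Objective 2.3.1.2) compares Arms 1 and 2 on the cumulative proportion with a qualifying Grade 3 or higher event, using the Kaplan-Meier estimator at week 65. On censoring it says: "Participants who have not experienced an event will be censored at the last completed study visit". On reporting: "We will present the point estimate and 90% two-sided confidence intervals for the difference in cumulative proportions". For people who leave early, "missing observations after discontinuation that would be relevant to the variable are considered missing completely at random".

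One departure from that assumption is specified: "Sensitivity analyses will consider participants who discontinue follow-up before week 65 as having at least one Grade 3 or higher adverse event". Nothing limits it to one arm.

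The supplementary analyses change the time horizon and leave the dropout assumption as it is: "we will also estimate the Kaplan-Meier proportions and confidence intervals for the outcome measure up to week 13, and up to week 26".

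SAP Section 2.4 shows which direction of difference the trial was sized to see. Its table "gives the power we would have to detect that Arm 1 is inferior to Arm 2 assuming a two-sided type 1 error of 0.10", with "10% probability of developing an AE in the SOC Arm, and varying probabilities (15-30%) of developing an AE in experimental Arm". It gives no dropout rate for safety follow-up; its 10% allowance is for unevaluable culture results in the efficacy comparison.

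**The concern.** The reported effect measure is a difference, and the difference of interest is an excess in Arm 1. A missing-data sensitivity analysis should ask whether that excess could be larger than the main analysis shows. Giving every leaver an event raises both arms' rates at once. Whether the difference then grows or shrinks is decided by the balance of dropout, not by how pessimistic the assumption is about Arm 1.

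What is at stake is interpretation. If leavers are counted as events and the difference gets smaller, a reader may take this as a worst case survived. It would only mean that Arm 1 dropout was not sufficiently greater than Arm 2 dropout.

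**Working it through.** **Inputs.** From SAP Section 2.4: 100 in Arm 1, 50 in Arm 2, two-sided alpha 0.10, p2 = 0.10, and p1 = 0.15, 0.20, 0.25 or 0.30. Assumed, because the documents give no figure: dropout before week 65 of d1 in Arm 1 and d2 in Arm 2, between 5% and 20%, independent of adverse events. Simple proportions stand in for Kaplan-Meier estimates.

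**The plan's own figures.** A two-proportion normal test with continuity correction reproduces the power table. For p1 = 0.20:

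- pooled p = (100×0.20 + 50×0.10)/150 = 0.1667
- standard error under the null = √(0.1667×0.8333×0.03) = 0.0645
- standard error under the alternative = √(0.20×0.80/100 + 0.10×0.90/50) = 0.0583
- continuity correction = 0.5×(1/100 + 1/50) = 0.015
- power = Φ[(0.10 − 0.015 − 1.645×0.0645)/0.0583] = 0.358

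The SAP states 0.36. The four rows come out at 0.132, 0.358, 0.636 and 0.849, against the stated 0.13, 0.36, 0.64 and 0.85. The planning case is therefore read correctly.

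**Effect of the rule.** If all leavers count as events, each arm's rate becomes

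p′ = p + (1 − p)d

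and the difference becomes

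D′ = (p1 − p2) + d1(1 − p1) − d2(1 − p2).

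With equal dropout, D′ = (1 − d)(p1 − p2). In general D′ is smaller than the true difference whenever d1 < d2(1 − p2)/(1 − p1). For 20% v 10% and d2 = 10%, that threshold is 0.10×0.90/0.80 = 11.25%. For p1 = 15%, 25% and 30% it is 10.6%, 12.0% and 12.9%.

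**Results for 20% v 10% (true difference 0.10).** The last column counts leavers as events in Arm 1 and, unless they already had an event, as non-events in Arm 2. The Arm 2 rate is then p2 if every event among leavers came before they left, or (1 − d2)p2 if none did, so a range is shown.

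| Dropout, Arm 1/Arm 2 | Arm 1 p′ | Arm 2 p′ | D′ under the SAP rule | Asymmetric bound |
|---|---|---|---|---|
| 10%/10% | 0.280 | 0.190 | 0.090 | 0.180 to 0.190 |
| 8%/15% | 0.264 | 0.235 | 0.029 | 0.164 to 0.179 |
| 5%/15% | 0.240 | 0.235 | 0.005 | 0.140 to 0.155 |
| 10%/20% | 0.280 | 0.280 | 0.000 | 0.180 to 0.200 |
| 15%/10% | 0.320 | 0.190 | 0.130 | 0.220 to 0.230 |
| 20%/10% | 0.360 | 0.190 | 0.170 | 0.260 to 0.270 |

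First row as an example: 0.20 + 0.80×0.10 = 0.280; 0.10 + 0.90×0.10 = 0.190; D′ = 0.090. The bound runs from 0.280 − 0.10 = 0.180 to 0.280 − 0.90×0.10 = 0.190.

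Put another way, let π1 and π2 be the event probabilities assumed for leavers without an event. The SAP's rule is the single corner π1 = π2 = 1. The corner least favourable to Arm 1 is π1 = 1, π2 = 0, and it is not planned.

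**The case against.** A reader might infer that the rule always pulls the difference toward zero, is anti-conservative for the experimental regimen, or hides real harm. The documents do not support any of these.

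- **Direction.** If toxicity drives people out of Arm 1, Arm 1 dropout rises and the rule moves the difference against Arm 1 (0.130 and 0.170 in the last two rows). This stands.
- **Size.** Equal dropout shrinks the point estimate only by the factor 1 − d, so 0.100 becomes 0.095 to 0.080 for dropout of 5% to 20%. The near-zero results need Arm 2 to lose about two to three times the fraction that Arm 1 loses, and no figure in the documents supports such rates. This stands. Letter of Amendment #1 adds follow-up contacts in Arm 1 only, which could affect retention by arm, but the direction is unknown.
- **Role.** The main Kaplan-Meier difference is still reported at weeks 13, 26 and 65 (SAP Section 6.6). Under the independence assumed here it still estimates 0.10. SAP Section 2.3 reserves formal testing for the primary efficacy objective, and no safety margin or pass rule depends on the sensitivity result. The risk is misreading, not a wrong decision.
- **Existing information.** Off-study reasons and last visit week are to be tabulated by arm (SAP Sections 6 and 6.3). That exposes an imbalance but does not show its effect on the difference.
- **The bound is harsh.** With no true excess (10% in both arms) and 10%/10% dropout it gives 0.19 − 0.10 = 0.09 up to 0.19 − 0.09 = 0.10. It must be labelled as extreme, and this is why a tipping-point table is needed beside it.

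A reader might also infer that people still in follow-up at the week 26 data cut would be counted as events. On the ordinary meaning of discontinuing they have not done so, and the point does not rest on this.

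**Conclusion.** The point holds in a limited form. The one missing-data sensitivity rule specified for the primary safety difference is a worst case for each arm's rate and not for the difference. Depending on assumed dropout, it turns a true 0.10 into anything from 0.000 to 0.170 in the cases shown, while a bound directed at Arm 1 harm lies between 0.140 and 0.270. It therefore cannot establish whether the finding on Arm 1 harm is robust to unfavourable missingness, and a shrunken result could give false reassurance.

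This rests on assumed dropout rates, on dropout independent of adverse events, and on simple proportions. That no other rule exists was checked against the SAP and Letter of Amendment #1 only; the full protocol version 2.0 and the Analysis Implementation Plan were not available. The main estimate is unaffected, so this is a cheap improvement and not a flaw in the primary analysis.

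**What to change.** Keep the both-arms rule if the team wants it, described as a worst case for each arm's rate. In SAP Section 5.1.1 (Objective 2.3.1.2) add:

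1. A bound in which participants who leave follow-up without a prior qualifying event count as events in Arm 1 and as non-events in Arm 2. Events observed before leaving are kept in both arms, and the result is labelled an extreme bound.
2. A tipping-point table in which the event probability assumed after dropout is varied separately in each arm, showing the difference and its 90% confidence interval in each cell.

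No new data are needed. The cost is a few lines of SAP text and one small table. The safety statement may look less favourable to Arm 1.
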